**Table CGAN. 5.7 Criteria for Treatment Emergent Changes in ECG Intervals and Heart Rate**

Parameter	Direction	Criteria	
Heart Rate (bpm)	Low	<50 and decrease $\geq 15$	
	High	>100 and increase $\geq 15$	
PR Interval (msec)	Low	<120	
	High	$\geq 220$	
QRS Interval (msec)	Low	<60	
	High	$\geq 120$	
QTcF (msec)	Low	Males: <330	Females: <340
	High	Males: >450	Females: >470
	PCS High	>500msec	
	Increase	Increase >30 msec	
		Increase >60 msec	
Increase >75 msec			
QTcLCTPB (msec)	Low	Male (All ages): <330;	Female (All ages): <340
	High	Male Age (yrs): criteria <18: >444 18-25: >449 26-35: >438 36-45: >446 46-55: >452 56-65: >448 >65: >460	Female Age (yrs): criteria <18: >445 18-25: >455 26-35: >455 36-45: >459 46-55: >464 56-65: >469 >65: >465
	PCS High	>500 msec	
	Increase	Increase >30 msec	
		Increase >60 msec	
Increase >75 msec			

Abbreviations: msec = millisecond; PCS = Potentially Clinically Significant; QTcF= The Fridericia's corrected QT interval; QTcLCTPB = The Large Clinical Trial Population Based QT Correction; yrs = years.

In addition, summary of qualitative ECG abnormalities (SP III with Fisher's exact test and SP IV without test) will be conducted which will include summaries of 11 ECG categories (Axis, Rhythm, Conduction, Ischemia, Infarction, Injury, Morphology, U-waves, T-waves, ST Segment, and Other Abnormalities) of qualitative findings at any time post-baseline for two population:

[1] Subjects who are baseline normal for a category,

[2] Subjects who are baseline normal for all of 11 categories.

Note that the output [1] contains overall interpretation result.

For SPIII and SP IV summaries, the baseline qualitative ECG status is defined as the status at last available qualitative ECG assessment during the baseline period (assessment day  $\leq$  Visit 3 for SP III, and assessment day  $\leq$  Visit 12 for SP IV). A category is a collection of possible descriptions (findings) of one qualitative aspect of an ECG. A category name is the name of the qualitative aspect of the ECG (for example, Rhythm, Conduction, Morphology, Ischemia, and so forth). A finding is 1 of the possible specific descriptions (for example, Sinus Bradycardia, Acute Septal Infarction) within a category.

Listing of Abnormal Qualitative ECG by Finding Category will be created (SP III, SP IV combined)

#### **5.5.12.1.5. Laboratory Tests**

The incidence rates of patients with treatment emergent abnormal, high, or low laboratory values based on Covance reference ranges at any time post-baseline will be assessed using the Fisher's exact test for each laboratory test for SP III and no tests for SP IV.

Patients will be defined as having a treatment emergent low value if they have all normal or high values at baseline, followed by a value below the lower reference limit at any post-baseline visit. Patients with all normal or high values at baseline (no low values) will be included in the analysis of treatment emergent low laboratory values. Patients will be defined as having a treatment emergent high value if they have all normal or low values at baseline, followed by a value above the upper reference limit at any post-baseline visit. Patients with all normal or low values at baseline (no high values) will be included in the analysis of treatment emergent high laboratory values.

For analytes simply classified as normal or abnormal, patients will be defined as having a treatment emergent abnormal value if they have all normal values at baseline, followed by an abnormal value at any post-baseline visit. Patients with all normal values at baseline will be included in the analysis of treatment emergent abnormal laboratory values.

The incidence of patients with the following elevations in hepatic laboratory tests at any time post-baseline will also be summarized and compared between treatment groups using the Fisher's exact test for SP III and no tests for SP IV.

- The percentages of patients with an alanine aminotransferase (ALT) measurement greater than or equal to 3 times (3 $\times$ ), 5 times (5 $\times$ ), and 10 times (10 $\times$ ) the Covance upper limit of normal (ULN) during post-baseline period will be summarized for all patients with a post-baseline value.

- The percentages of patients with an aspartate aminotransferase (AST) measurement greater than or equal to 3 times (3×), 5 times (5×), and 10 times (10×) the Covance upper limit of normal (ULN) during post-baseline period will be summarized for all patients with a post-baseline value.
- The percentages of patients with an Alkaline phosphatase (ALP) greater than or equal to 2 times (2×) the Covance ULN during post-baseline period will be summarized for all patients with a post-baseline value.
- The percentages of patients with a total bilirubin (TBIL) measurement greater than or equal to 2 times (2×) ULN during post-baseline period will be summarized for all patients with a post-baseline value.

Hy's law is defined as the combination of elevation of  $ALT \geq 3 \times ULN$  and  $TBIL \geq 2 \times ULN$ , in the absence of significant cholestasis ( $ALP < 2 \times ULN$ ).

The analysis of elevation in ALT, AST, ALP, and TBIL will contain three subsets:

- Patients whose nonmissing maximum baseline value is less than or equal to  $1 \times ULN$  for ALT, AST, ALP, and TBIL.
- Patients whose nonmissing maximum baseline value is greater than  $1 \times ULN$  for ALT, AST, ALP, and TBIL, and at the same time less than or equal to  $2 \times ULN$  for ALT and AST,  $1.5 \times ULN$  for ALP and TBIL.
- Patients whose nonmissing maximum baseline value is greater than  $2 \times ULN$  for ALT and AST,  $1.5 \times ULN$  for ALP and TBIL.

Note that patients with no corresponding postbaseline values will be excluded.

A listing of Subjects with abnormal Laboratory Results will be created. (SP III, SP IV combined)

A listing of Subjects with abnormal Hepatic Laboratory Results will be created. (SP III, SP IV combined)

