8.1. Discontinuation from Study Treatment

8.1.1. *Permanent Discontinuation from Study Treatment*

Discontinuation of the investigational product for abnormal liver tests **should be considered** by the investigator when a patient meets one of the following conditions after consultation with the Lilly designated medical monitor:

- ALT or aspartate aminotransferase (AST) >8X ULN
- ALT or AST >5X ULN for more than 2 weeks
- ALT or AST >3X ULN and TBL >2X ULN or prothrombin time >1.5X ULN
- ALT or AST >3X ULN with the appearance of fatigue, nausea, vomiting, right upper-quadrant pain or tenderness, fever, rash, and/or eosinophilia (>5%)
- ALP >3X ULN
- ALP >2.5X ULN and TBL >2X ULN
- ALP >2.5 ULN with the appearance of fatigue, nausea, vomiting, right quadrant pain or tenderness, fever, rash, and/or eosinophilia (>5%)

8.1.2. *Discontinuation of Inadvertently Enrolled Patients*

If the sponsor or investigator identifies a patient who did not meet enrollment criteria and was inadvertently enrolled, a discussion must occur between the sponsor CRP and the investigator to determine if the patient may continue in the study. If both agree it is medically appropriate to continue, the investigator must obtain documented approval from the sponsor CRP to allow the inadvertently enrolled patient to continue in the study, with or without treatment with investigational product.

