9.4.4. Safety Monitoring

Lilly will periodically review evolving aggregate safety data within the study by appropriate methods.

Investigators are responsible for monitoring individual patient safety throughout the trial. If a study patient/subject experiences elevated ALT $\geq 3X$ ULN, ALP $\geq 2X$ ULN, or elevated TBL $\geq 2X$ ULN, clinical and laboratory monitoring should be initiated by the investigator. Details for hepatic monitoring depend upon the severity and persistence of observed laboratory test abnormalities. To ensure patient/subject safety and to comply with regulatory guidance, the investigator is to consult with the Lilly CRP/CRS regarding collection of specific recommended clinical information and follow-up laboratory tests (see [Appendix 4](#)).

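### The SAP's only combined liver category requires raised ALT, so a joint AST and bilirubin elevation with ALT below 3×ULN is not tabulated as a combined event

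*SAP*

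**What the plan says.** In SAP 5.5.12.1.5 (Laboratory Tests), Hy's "law is defined as the combination of elevation of" ALT ≥3×ULN and total bilirubin ≥2×ULN, "in the absence of significant cholestasis", which is specified as ALP <2×ULN. The definition does not mention AST, and the section does not name the table that will report it.

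The same section plans single-analyte summaries: "The incidence of patients with the following elevations in hepatic laboratory tests at any time post-baseline will also be summarized", with Fisher's exact test in Study Period III and no test in Study Period IV. They include AST ("The percentages of patients with an aspartate aminotransferase (AST) measurement greater than or equal to 3 times", with further cut-offs at 5 and 10 times) and bilirubin ("The percentages of patients with a total bilirubin (TBIL) measurement greater than or equal to 2 times"). ALT has the same three cut-offs as AST, and ALT and AST share the same baseline subsets. A listing of patients with abnormal hepatic results, covering Study Periods III and IV, is also planned; its contents are not specified.

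Protocol 8.1.1 gives seven liver-test conditions for considering "Discontinuation of the investigational product for abnormal liver tests". One of them is "ALT or AST >3X ULN and TBL >2X ULN or prothrombin time >1.5X ULN". It has no ALP condition.

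**The concern.** A combined definition exists to show that transaminase and bilirubin rose in the same patient. The SAP handles AST in parallel with ALT in the single-analyte summaries and the baseline subsets, but drops it from the combination. SAP Section 3 records that the Hy's law definition was modified for Version 2 and gives no reason, so the documents do not explain why AST is left out.

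The event is rare and a zero is likely to be read as reassurance. If a patient had a joint rise carried by AST, the combined count would still read zero, and a reader would have to find the case by searching a listing. SAP 5.6 says that the Study Period III outputs are meant for regulatory submission in Japan, so the summary tables will carry weight.

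**Working it through.** The plan gives no figure to reproduce. The check is a comparison of rules, with all values in multiples of ULN.

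**Inputs**
- SAP rule (SAP 5.5.12.1.5): ALT ≥3 and TBIL ≥2 and ALP <2.
- Protocol rule, bilirubin branch (Protocol 8.1.1): (ALT >3 or AST >3) and TBL >2. The prothrombin-time branch is set aside because the point concerns bilirubin.
- Single-analyte summaries (SAP 5.5.12.1.5): AST ≥3; TBIL ≥2.

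**Step 1: one patient.** Take ALT 2.9, AST 3.5, TBIL 2.5, ALP 1.
- SAP rule: 2.9 ≥3 is false, so not met.
- Protocol rule: 3.5 >3 and 2.5 >2, so met.
- Single-analyte summaries: 3.5 ≥3 and 2.5 ≥2, so counted in both.

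The patient is counted twice singly and not at all in combination.

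**Step 2: can the single tables recover the joint count?** If *a* of *n* patients have AST ≥3 and *b* have TBIL ≥2, the number with both lies between max(0, a + b − n) and min(a, b). With a = b = 1 and a planned arm of n = 113, this runs from max(0, −111) = 0 to 1. The tables cannot say whether it is one patient or two.

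**Step 3: all patterns on a grid.** ALT and AST each take 1, 2.9, 3 or 3.5; TBIL and ALP each take 1, 1.9, 2 or 2.5. This gives 4 × 4 × 4 × 4 = 256 cells. The protocol rule needs TBIL = 2.5 (1 value) and ALT or AST = 3.5 (4 + 4 − 1 = 7 pairs), at any ALP (4 values): 7 × 1 × 4 = 28 cells.

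| Cells meeting the protocol rule | Number |
|---|---|
| Also meet the SAP rule | 10 |
| Fail it because only AST is raised (ALT <3, ALP <2) | 4 |
| Fail it because ALP ≥2 | 14 |
| Total | 28 |

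**Step 4: effect of adding AST.**
- (ALT or AST) ≥3, TBIL ≥2, ALP <2: 10 + 4 = 14 of 28 cells.
- The same without the ALP condition: 28 of 28 cells.

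These are counts of logical patterns and say nothing about how often each occurs in patients.

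**The case against.** The strongest reply is that no patient is lost. Someone with raised AST and bilirubin is in both single-analyte summaries and within the scope of the hepatic listing, and with so few cases a listing is a reasonable place to see that both results belong to one person. During the trial, bilirubin ≥2×ULN is by itself enough under Protocol 9.4.4 that "clinical and laboratory monitoring should be initiated by the investigator". This stands. A reader might infer from the ALT-only definition that such patients are counted nowhere, and the documents do not support that. What remains is that no planned summary shows the joint event, and the content of the listing is left open.

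A reader might also infer that the SAP contradicts the protocol. It does not. The condition in Protocol 8.1.1 prompts a clinical decision; it is not an analysis definition. It also differs in structure, with a prothrombin-time branch and no ALP condition. Other hepatic rules in the protocol name ALT without AST: exclusion criterion [25] and the monitoring trigger in 9.4.4. The SAP's ≥ cut-offs for ALT and bilirubin match those in 9.4.4, not the > limits in 8.1.1.

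Finally, adding AST would not by itself bring the two rules into line. In the grid, 14 of the 18 mismatched patterns come from the ALP condition. That objection is correct and is why the fix shows the count both ways.

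**Conclusion.** The point holds as a small reporting gap. A patient with AST ≥3×ULN and bilirubin ≥2×ULN but ALT <3×ULN is not tabulated as a combined elevation, and the separate AST and bilirubin percentages cannot show that both occurred in one person.

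The size of the effect cannot be estimated, because the documents give no rate for such elevations, and any expected number of cases would be an assumption. For scale only, one such patient in a galcanezumab arm at planned enrolment would change a combined percentage from 0 to 1/113 = 0.9%. No efficacy result is affected and no stated analysis rule is broken. The conclusion assumes that the Hy's law definition in SAP 5.5.12.1.5 will be reported as written and that no unlisted output already combines AST with bilirubin.

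**What to change.** Keep the ALT-based Hy's law definition. In the hepatic elevation summary of SAP 5.5.12.1.5, add a count of patients with (ALT or AST) ≥3×ULN and total bilirubin ≥2×ULN, in two rows: with ALP <2×ULN and without any ALP condition. Name the table that carries these rows and the existing definition. State whether the elevations must come from the same sample or may occur at any time after baseline, since the definition does not say.

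The cost is one SAP line and one derivation. ALT, AST, total bilirubin and ALP are all in the clinical chemistry panel (Protocol Appendix 2) and are drawn at the same visits, so no new data are needed. The downside is that an AST rise of non-hepatic origin may add a case for medical review. The change concerns reporting only and leaves the clinical stopping criteria as they are.

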#### **5.5.12.1.6. Immunogenicity**

To evaluate the changes in immunogenicity data of

- Anti-LY2951742 Antibody (hereafter "Anti-Drug Antibody (ADA),")
- Neutralizing ADA (hereafter "Neutralizing Antibody (NAb)") after treatment,

the statistical analyses (Fisher's exact test) are planned for comparison between treatment groups.

The summary (baseline=Visit 3) will be created for

1. SP III (safety population)
2. SP III (ADA follow-up cohort)
3. SP III and SP IV combined (ADA follow-up cohort)

Analysis of each period include:

- The incidence of “ADA positive (%)” and “ADA positive and NAb Positive (%)” during baseline (Visit 3).
  
- The incidence of treatment emergent ADA (TE ADA) between treatment groups. The baseline and post-baseline definitions for each study period is shown in [Table CGAN. 5.4](#). Treatment emergent ADA will be defined as any of the following:
  - A negative baseline result and a positive post-baseline ADA result with a titer  $\geq 20$ . This is also called treatment-induced ADA.
  - A positive baseline result and a positive post-baseline ADA result with a  $\geq 4$ -fold increase in titers (for example, baseline titer of 10 increasing to  $\geq 40$  post-baseline). This is called treatment-boosted ADA.
  
- The incidence of TE-ADA and NAb Positive combined.

Note that TE-ADA can happen at multiple visits during SP III (or SP III and SP IV combined) because the judgement is solely based on comparison between the particular visit and the baseline (Visit 3) (i.e., listings may contain multiple TE-ADA time points, although one TE-ADA point is enough to be considered being TE-ADA subject with that TE-ADA.)

The following will also be created:

- Listing of subjects with TE-ADA at any time during study (SP III and SP IV combined), NAb Status will also be displayed.
- Listing of subjects with ADA detected at any time during study (SP III and SP IV combined) excluding subjects with TE-ADA.
- Listing of subjects with TEAEs of hypersensitivity reactions or injection site reactions or ADA present at any time (SP III, SP IV).

#### 5.5.12.2. Continuous Safety Measures

Analyses of continuous safety data will be conducted on safety patients who have a baseline and at least one post-baseline observation for each analysis period (SP III, SP IV, SPIII and SP IV combined).

When mixed model repeated measures analysis is used, values from unscheduled visits will be ignored and only value collected at scheduled visit will be used.

For the following continuous safety measures, changes from last baseline value to LOCF will be assessed using an ANCOVA model as described in [Section 5.5.1.1](#) with the fixed categorical effects of treatment, baseline value as the covariate:

- laboratory for SP III
- laboratory for SP IV

- weight for SP III
- ECG for SP III
- ECG for SP IV

If repeat laboratory values, weight or ECG exist at the same scheduled visit, only the last nonmissing value at a visit (selected by using the variable with highest lab sequence ID) will be used in the ANCOVA analysis for mean change from the last baseline value to LOCF endpoint.

For the following safety measures, the mean change from baseline will be analyzed using a mixed model repeated measures analysis. The analysis will include the fixed categorical effects of treatment, month and treatment-by-month interaction, as well as the continuous fixed covariates of baseline value and baseline-by-month interaction:

- vitals (SBP, DBP, Pulse) for SP III
- vitals (SBP, DBP, Pulse) for SP III and SP IV combined (safety population)
- weight for SP III and SP IV combined (safety population)
- temperature for SP III
- temperature for SP III and SP IV combined (safety population)

### **5.5.13. Subgroup Analyses**

Subgroup analyses will be performed for primary efficacy measure (change from baseline in the number of monthly migraine headache days) only for the ITT patients in the 6-month treatment phase unless otherwise specified. [Table CGAN. 5.8](#) provides definitions for each subgroup variable. Subgroup variables are usually selected if they are potentially prognostic or predictive. A subgroup variable is prognostic if values of the subgroup variable predict the change in efficacy measures regardless of the treatment group assignment. A subgroup variable is predictive if values of the subgroup variable predict heterogeneous treatment effect. Current understanding is that demographic subgroup variable sex is not prognostic nor predictive. But they are standard subgroup variables needed for regulatory submission. The rest of subgroup variables determined before Visit 3 injection are expected to be prognostic. The purpose of the analyses for these subgroup variables is to assess the consistency of treatment effects across the different values of each subgroup variable.

Table CGAN. 5.8 Definition of Subgroup Variables

Subgroup Variable	Categories
Sex	Male, female
Baseline category of MHD (Visit 2 to Visit 3)	2 levels of baseline migraine frequency : 
 
• <8 migraine headache days per 30-day period
 
• ≥8 migraine headache days per 30-day period
 

Treatment resistant status (Visit 1)	Treatment resistant status about whether a patient has failed two or more prophylactic treatments (migraine preventive therapy): Yes vs No
Having aura or not (during baseline Visit 2 to Visit 3 period)	Yes vs No (a patient with aura is defined as a patient who answers “yes” to at least one day of ePRO Question 12 “Yesterday, did you experience aura?” during prospective baseline period)
Baseline anti-drug antibody status (Visit 3)	Any confirmed positive anti-drug antibody at baseline (Yes vs No)
Neutralizing anti-drug antibody status (SP II and SP III)	Any positive neutralizing anti-drug antibody time point (Yes vs No) – note that neutralizing anti-drug antibody assays are performed only on confirmed-positive anti-drug antibodies
Treatment-emergent anti-drug antibody status (SP III)	Any treatment-emergent anti-drug antibody (Yes vs No)
Baseline body weight (last observation before Visit 3 injection)	2 levels (weight ≤ median, median < weight).

Abbreviations: MHD = migraine headache days.

For subgroup analyses, the subgroup-by-treatment interaction will be tested at a 2-sided 0.1 significance level. Treatment group differences will be evaluated within each category of the subgroup variable.

The subgroup analyses for primary will be conducted using MMRM. The same MMRM model as described in Section 5.5.10.1 will be used with terms of subgroup, subgroup-by-treatment, subgroup-by-month, and subgroup-by-treatment-by-month interactions added as additional covariates. In this analysis, the p-value for the subgroup-by-treatment, subgroup-by-month, and subgroup-by-treatment-by-month interactions will be reported.

For the analysis within a subgroup using MMRM, the LSMean change estimates as well as the treatment comparisons within each subgroup will be conducted with the data within that specific subgroup. The MMRM model will be the same as described in Section 5.5.10.1. For each category of the subgroup variable, comparisons between each treatment group with placebo will be assessed during the 6-month post-baseline period.

50% response rate (one of the key secondary analysis) will be performed by the treatment resistant status subgroup, (simply using 2 different subgroups with the same covariates)

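### Two subgroup variables fixed after dosing (treatment-emergent and neutralizing antibody status) are tested as if they were baseline subgroups

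*SAP*

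**What the plan says.** Table CGAN. 5.8 in SAP 5.5.13 lists eight subgroup variables for the primary efficacy measure. Six are known at or before the Visit 3 injection: sex, baseline migraine-day category, treatment-resistant status, aura, baseline antibody status and body weight. The other two are not:

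- Treatment-emergent antibody (TE-ADA) status over Study Period III: "Any treatment-emergent anti-drug antibody (Yes vs No").
- "Neutralizing anti-drug antibody status (SP II and SP III"), where any positive time point counts.

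Protocol 10.3.6.2 (Table CGAN.10.2) lists the same two variables.

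The method is stated once, with no exception:

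- "For subgroup analyses, the subgroup-by-treatment interaction will be tested at a 2-sided 0.1 significance level".
- From the primary MMRM with subgroup terms added, "the p-value for the subgroup-by-treatment, subgroup-by-month, and subgroup-by-treatment-by-month interactions will be reported".
- "For each category of the subgroup variable, comparisons between each treatment group with placebo will be assessed during the 6-month post-baseline period".

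On purpose, 5.5.13 first says that subgroup variables are usually chosen because they may be prognostic or predictive. It then deals with sex and adds: "The rest of subgroup variables determined before Visit 3 injection are expected to be prognostic". The next sentence gives the aim for these variables: "to assess the consistency of treatment effects across the different values of each subgroup variable".

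**The concern.** Randomisation makes the arms comparable within categories fixed before the first dose. It does not do so within categories that depend on what happened after it. A TE-ADA-positive patient on galcanezumab formed antibodies after exposure to the drug. A TE-ADA-positive patient on placebo met the same titer rule without exposure. The two groups need not be alike, and the same holds for the remaining negatives.

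If antibody formation is related to outcome for other reasons, the dose-versus-placebo contrast within a category can be biased. If that relation differs between arms, the interaction test is biased too. A small p-value could then be read as antibodies changing the treatment effect, and a large one as reassurance. Neither reading would be justified.

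**Working it through.** **Timing of classification**

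1. SAP 5.5.12.1.6 defines treatment-induced TE-ADA as "A negative baseline result and a positive post-baseline ADA result with a titer" of at least 20. Treatment-boosted TE-ADA needs at least a 4-fold rise after baseline. SAP Table CGAN. 5.4 sets baseline at Visit 3 and post-baseline at Visits 3.01-12. A patient can therefore become Yes only after dosing.
2. The Schedule of Activities (protocol section 2) takes immunogenicity samples in the treatment period at Visits 3, 4, 5, 6, 7 and 12, before dosing at dosing visits. Only the Visit 3 sample precedes the first dose. Neutralizing status over Study Periods II and III therefore mixes one pre-dose result with later ones.
3. A patient first positive at Visit 12 is labelled Yes for migraine days already recorded over Months 1-6.
4. The expectation of a prognostic role is limited to variables known before the Visit 3 injection. If the consistency aim that follows covers only those variables, the two antibody variables have no stated aim beyond the general selection basis. If it covers all eight, the aim cannot be met for these two.

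**Scale**

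The plan gives no expected count or power for subgroups. Its sample-size figure supplies a scale: effect size 0.36, 225/113/113 patients, 15% discontinuation, about 88% power. A two-sided Dunnett test (critical value 2.226) on 191.25/96.05/96.05 patients gives 89.6%, so that figure reproduces and is not in dispute.

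**Size of the bias**

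All antibody rates and differences here are assumptions. Let p be the positive rate in an arm and d the positive-minus-negative difference, in SD of change in migraine days, that is not caused by the antibody. Subscript A is active and P is placebo. With arm means held fixed:

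- bias in Yes = (1 - pA)dA - (1 - pP)dP
- bias in No = -(pA·dA - pP·dP)
- bias in the interaction = dA - dP

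With pA from 5% to 12% and pP from 0.5% to 5%:

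- dA = dP = 0.5: the interaction bias is 0. The category bias is largest at pA = 0.12, pP = 0.005, where Yes = 0.88 × 0.5 - 0.995 × 0.5 = -0.0575, and No is the same.
- dA = 0.5, dP = 0: Yes = 0.95 × 0.5 = 0.475 to 0.88 × 0.5 = 0.44. No = -0.025 to -0.06. The interaction bias is 0.50.
- dA = dP = 0: no bias.

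**Rejection rate of the 0.10 interaction test**

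Three arms give 2 degrees of freedom. With weights wA = 113·pA(1 - pA) per dose and wP = 225·pP(1 - pP), the noncentrality is (dA - dP)² × 2wA·wP / (2wA + wP), and the critical value is 4.605. For pA = 0.05 and pP = 0.005, wA = 5.37 and wP = 1.12. The noncentrality is 0.25 × (10.73 × 1.12)/(10.73 + 1.12) = 0.25, and rejection is 12.9%.

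| Placebo rate | dA - dP = 0.5 | dA - dP = 0.25 |
|---|---|---|
| 0.5% | 13% | 11% |
| 1% | 15-16% | 11-12% |
| 2% | 19-21% | 12-13% |
| 5% | 26-32% | 14-15% |

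Each range covers active rates of 5-12%. These figures use one averaged outcome and full planned numbers, not the full MMRM. A simulation of 4,000 trials per setting with the same true effect in every patient gave 13.8-30.6% at 0.5 SD, and 10.6-11.0% when the difference was equal in all arms.

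A second simulation compared one dose with placebo. On active drug, TE-ADA shared a latent factor with outcome (assumed correlations 0.5 with TE-ADA and 0.3-0.5 with outcome). It used rates of 5-15% on active and 2-5% on placebo. The test rejected in 14-30% of trials, and the Yes contrast moved from about -0.36 to between -0.12 and +0.17 SD. With no link to outcome, rejection was 10-11%.

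**The case against.** The strongest objection is that removing placebo would cure nothing. A positive-versus-negative comparison within the galcanezumab arms carries bias dA, while the interaction carries dA - dP. With dA = 0.5 and dP = 0 both are 0.50 SD. With dA = dP = 0.5 the interaction bias is zero and the within-active comparison is still off by 0.50 SD. This stands, and the fix below keeps placebo in view.

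Second, the plan has a reason to look. A secondary objective (protocol Table CGAN.4.1, SAP Table CGAN. 4.2) covers the consequences of antibodies, and these subgroups are the only visible SAP analysis linking antibody status to efficacy. That supports keeping the display. It does not support testing it as effect modification.

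Third, the magnitudes are assumed, and a dA of 0.5 exceeds the whole planned effect of 0.36. The 32% needs 12% positive on active together with 5% on placebo. At placebo rates of 0.5-2% and 0.5 SD the range is 13-21%. This also stands.

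Fourth, small categories make any such estimate imprecise. That is true, but baseline antibody status would share the problem, so it is no argument specific to these two variables.

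A reader might also infer that SAP 5.8.1 releases these results at the interim lock, since it lists the subgroup analyses there. The same section places antibody-related analysis at the final lock, so the timing needs no change.

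**Conclusion.** The point holds, with limited scope. For TE-ADA status, and in part for neutralizing status, the interaction test and the dose-versus-placebo contrasts within category are not protected by randomisation and cannot show consistency or inconsistency of treatment effect. The pre-injection rationale in 5.5.13 does not cover these variables.

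The size cannot be fixed from the documents. Under the assumed rates, a difference of 0.25-0.5 SD more on active than on placebo raises the nominal 10% rejection rate to about 11-32%. A difference equal in all arms gives no inflation.

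A reader might infer that the trial's main conclusion or its type I error is at risk. The documents do not support that: these are two of eight supportive subgroup variables, with no decision rule attached in the visible text. Nor does the point touch the antibody incidence comparisons and listings in SAP 5.5.12.1.6. Redacted text and the separate PK/PD analysis plan may hold other antibody-efficacy analyses, which cannot be judged here.

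**What to change.** In SAP 5.5.13, for TE-ADA and neutralizing status only:

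- Do not perform or report the interaction tests or the within-category treatment p-values.
- Present change in migraine headache days by antibody status in every arm, including placebo where numbers allow, with estimates and confidence intervals. Label the tables post-randomisation, descriptive and non-causal, and tie them to the objective on consequences of antibodies.
- Do not present the positive-versus-negative contrast within galcanezumab as less biased. It has its own confounding.
- Keep baseline antibody status (Visit 3) under the current model.
- Record the change in the SAP and/or the study report, as SAP 5.5.1 allows.

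The cost is SAP wording and two tables without p-values. No new samples are needed. The downside is that these two variables have no formal test and the estimates stay imprecise. At the assumed rates, 113 × 0.05 to 113 × 0.12 gives about 6-14 positives per dose, and 225 × 0.005 to 225 × 0.05 gives about 1-11 on placebo. The 95% half-width for a positive-group mean (1.96/√n) is then 0.53-0.82 SD per dose and 0.58-1.85 SD on placebo. At a placebo rate of 0.5% the chance of no placebo positive at all is 0.995^225 = 32%, and at 1% it is 10%.
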